#### a) Primary Outcomes

**Aim 1** Proportion of women with *Plasmodium falciparum* peripheral parasitemia by microscopy or PCR.

**Aim 2** Prevalence of a composite STI measure (GC, CT, syphilis infections) will be measured in both groups in late pregnancy (>35 weeks gestation) or at delivery and compared between the two groups.

[figure not shown]
**Aim 3** a) Mean infant birthweight; b) Proportion with adverse birth outcomes, including low infant birthweight (<2500 gm), miscarriage (<28 weeks), preterm delivery (<37 weeks), small for gestational age (SGA), stillbirth (>28 weeks), congenital anomaly at birth, early neonatal mortality (within 7 days); and c) maternal adherence to and tolerance of the prophylactic regimen (vomiting, rash/allergic reactions, dizziness, weakness).

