**d) 35-42 Week Visit**

Vitals and brief exam.

Testing: CBC, RDT, DBS and store, vaginal swab for GC/CT and store, anogenital swab for GBS, vaginal pH, slides and store, rapid syphilis test with RPR confirmation.

Questions will be asked by study staff and entered into a RedCAP database.

Treatment:

Malaria with positive RDT: Artesunate IV (dosing above). GC/CT/Syphilis (same day if possible). DOT of prophylaxis medications. Condoms and safe sex counseling will be provided.

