**e) Labor and Delivery Visit**

Vitals and brief exam.

Testing (if not performed at 35-42 weeks): CBC, thick smear, DBS and store, vaginal swab for GC/CT and store, anogenital swab for GBS, vaginal pH, slides and store, rapid syphilis test with RPR confirmation. Collect placentas, OK to refrigerate overnight.

Biopsy specimen placed in formalin and can be stored on site. Questions will be asked by study staff and entered into a RedCAP database.

Treatment:

Malaria with positive RDT or peripheral parasitemia: Artesunate IV. GC/CT/syphilis if not yet treated from prior visit or newly detected. Ampicillin IV for GBS positive (late pregnancy screen or L+D screen). Treat maternal/neonatal infection per routine.

Survey: FU survey with questions about medication adherence, tolerance, interim medications and source.

Study RN: outcome assessment form including infant weight with electric scale, GA, maternal/neonatal infection, surface examination for major congenital anomalies. Verify contact information – plan to call after 7 days to ask about neonatal mortality. Recommend infant HIV testing.

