**g) Follow Up Phone Call – within 6 weeks**

Women will be contacted by telephone to check in to see how mom and baby are doing and to document any new outcomes on the study outcomes form including hospitalizations and deaths.

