## **XII. DATA ANALYSIS AND MANAGEMENT**

Data management and analysis will be led by the University of Alabama at Birmingham under the supervision of the study PI ([name]).

The primary analysis will be by intention to treat for women who are randomized and receive at least 1 dose of study medication.

The “per protocol” analysis will be performed on women who came to at least one follow up visit following the enrollment visit, reported excellent (>90%) medication adherence, and had outcomes captured (ie – not lost to follow up).

**Statistical Analysis:** Descriptive statistics will be used to compare the study participants between each arm and the primary analysis will be intention-to-treat for the primary outcome of proportion of women with parasitemia. The analysis plan for categorical outcomes is chi-square, Fisher’s exact tests as needed for small sample sizes and we plan to use t-test and Wilcoxon Rank-Sum tests for continuous outcomes. Women will be considered lost to follow up if they do not have a study visit after 35 weeks or at delivery for outcome ascertainment.

For the secondary outcomes, the significance of differences in proportion will be explored using the Pearson’s  $\chi^2$  test or Fisher’s exact test. Multivariable regression modeling will be used to evaluate baseline factors associated with parasitemia if there is imbalance between the arms despite randomization. Potential covariates include age, parity, educational level, monthly income, marital status, history of negative birth outcomes, CD4 count, ART adherence, bed net usage, malaria treatment received and number of study visits. All analyses will be performed in SAS v 9.3.

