### XIII. STUDY TIMETABLE

	2017	2018	2019	2020
IRB Approval	X			
Hire Study Staff	X			
Training	X			
Enrollment		X	X	
Subject Follow Up		X	X	
Data Processing		X	X	
Data Analysis				X

- a) IRB Approval – see ethical considerations in subsequent section (Section XIV).
- b) Study Staff – One study nurse and one data manager will be hired at each facility and the current CHI-UAB Coordinator will assume the duties of study coordination at both sites. The study PI will be onsite several times a year for 1-2 months at a time during the study period. She will also be on site during training, study initiation and enrollment.
- c) Training – Before the trial begins, study nurses, coordinators, physician co-investigators and laboratory staff will undergo training on study procedures and data collection, including standardized testing methods for malaria and sexually transmitted infections and how to perform a surface examination for congenital anomalies at birth and collect placental biopsies.
- d) Enrollment and Follow Up – In 2014, Mboppi Hospital in Douala had more than 15,000 antenatal care visits and 4000 deliveries. Approximately 400 new pregnant patients are seen each month in clinic and approximately 24 women are HIV-infected (seroprevalence 5.9%). At the Baptist Hospital in Mutengene (BHM), the HIV seroprevalence is 10.2%, and there are 10 new HIV-infected women seen each month in clinic. Approximately 20% of women present for ANC care during their 1st trimester and 75% during the second trimester. Pregnant women routinely have 4 prenatal visits and clinic attendance rates are high with 80% facility delivery rates.

We plan to enroll approximately 18 women each month (12 in Douala, 6 in Mutengene) over an 18 month enrollment period to reach the 308 women needed. This will allow us to have 268 women with evaluable outcomes according to the power calculation stated above (this assumes 15% loss to follow up but we will strive for >95% subject retention).

- e) Data Processing and Analysis – After a three-month period for completion for data entry for the trial, the dataset will be locked and available for analysis. Approximately six months will be required to complete the final report and submit it for publication. Group meetings will be held to determine which manuscripts will be written and the appropriate team members for submitted abstracts and publications.

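### The single loss rule does not fit the Aim 3 birth outcomes: the per-protocol set drops recorded early pregnancy endings, all adverse, and counts a term visit before birth as capture

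*Combined protocol and SAP*

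**What the plan says.** Section XII defines loss once, for the whole trial: "Women will be considered lost to follow up if they do not have a study visit after 35 weeks or at delivery for outcome ascertainment". It builds the per-protocol set from women with at least one follow-up visit and reported adherence above 90% who "had outcomes captured (ie – not lost to follow up"). The intention-to-treat set is defined separately, as women randomized who took at least one dose, with no condition on loss.

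Section III.a lists the Aim 3 birth outcomes as primary. They include mean birthweight, stillbirth, congenital anomaly, "miscarriage (<28 weeks), preterm delivery (<37 weeks") and "early neonatal mortality (within 7 days").

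Several contacts can supply these outcomes. Section I.c names chart review. The visit table in Section VII schedules the outcomes form (Form 9) at sick, term, delivery and postpartum visits and at the follow-up call. At that call, within 6 weeks, staff are to "document any new outcomes on the study outcomes form including hospitalizations and deaths". Section VII.h adds infant contacts every three months up to one year. The "35-42 Week Visit" (Section VII.d) collects blood and swabs, normally before birth.

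**The concern.** The rule was evidently written for Aims 1 and 2, whose samples are taken at the term visit, at delivery or shortly after. For those aims, a visit after 35 weeks or at delivery is close to the same thing as an outcome. For Aim 3 it is not.

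The main worry is selection on the result. If a pregnancy ends early and away from the facility, the woman may never have a qualifying visit, yet the trial may know exactly what happened. Removing her from the per-protocol set removes an adverse outcome. Each removal takes one from both the numerator and the denominator of the adverse proportion, so that proportion can only fall. Aim 3 is there to describe fetal and neonatal safety, and early losses are part of what it should show.

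The lesser worry is the loss count. A woman can be retained by the rule with nothing known about the birth, so the reported loss figure is not the number of missing birth outcomes.

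**Working it through.** **1. The plan's own figures.** The loss allowance belongs to Aim 1 (Section XI: 30% versus 15%, two-sided 0.05, 80% power). The two-proportion formula gives 121 per arm without and 134 with continuity correction, so the stated 134 reproduces. Then 134 × 1.15 = 154.1, the stated 154 per arm, or 308 in total. None of this sizes Aim 3, and the point does not depend on it.

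**2. The rule applied case by case.**

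| Case | Visit after 35 weeks or at delivery? | Status under Section XII | Aim 3 pregnancy outcome |
|---|---|---|---|
| Ends before 28 weeks, no delivery visit; recorded at a sick visit, in the chart or by phone | No | Lost; out of per-protocol set | Known: miscarriage |
| Ends from 28 to before 35 weeks, no delivery visit; recorded as above | No | Lost; out of per-protocol set | Known: preterm delivery, live or stillborn |
| Seen at 36 weeks, delivers elsewhere, not reached again | Yes | Not lost, so treated as captured | Unknown |
| Delivers at the facility | Yes | Not lost | Known at birth |

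The first two rows cover every pregnancy that ends before 35 weeks. Under Section III.a each is a miscarriage (below 28 weeks) or a preterm delivery (below 37 weeks). No known outcome in these rows can be favourable, which is why the exclusion depends on the result.

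The postpartum visit (Section VII.f) is for women who did not deliver at the facility. If it is read as standing in for the delivery visit, women who attended it leave the first two rows.

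**3. Size of the main fault.** The documents do not give the share of pregnancies ending early, so this is illustration only. Number = N × p × a × k, with:
- N = 308 (Section XI);
- p = share ending early, assumed 5–10%;
- a = share of those away from the facility, assumed 20–50%;
- k = share of those recorded only by a route the rule does not count, assumed 25–75%.

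Low: 308 × 0.05 × 0.20 × 0.25 = 0.8. High: 308 × 0.10 × 0.50 × 0.75 = 11.6. That is about 1 to 12 of 308. The follow-up visit and adherence criteria would already exclude some of these women, so fewer are lost to this rule alone.

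**4. Size of the lesser fault.** Expected not lost: 308 × 0.85 = 261.8. Assume 5–20% of these deliver elsewhere and 10–50% of those are never reached. Section XIII.d's 80% facility delivery rate gives the 20%; the other figures are assumptions. Low: 261.8 × 0.05 × 0.10 = 1.3. High: 261.8 × 0.20 × 0.50 = 26.2.

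The high end is probably too high. The 80% rate describes the whole clinic, while participants must plan to deliver at the facility (Section V.b). Every woman with a delivery visit is not lost by definition, so births elsewhere should be under 20% of the women not lost.

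**5. Effect on the tests.** A woman with no birthweight contributes nothing to a t-test on birthweight or a chi-square on low birthweight, whatever her label. The lesser fault therefore changes the reported loss figure and hardly changes the tests. The main fault does change who is analysed in a per-protocol comparison.

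**The case against.** The best defence has four parts.

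*The primary analysis is intention to treat, and Section XII ties it to parasitemia.* This stands. The point reaches only supportive work and the loss count. Section XII also names no per-protocol analysis specific to Aim 3. However, it defines the per-protocol set without limiting it to one outcome.

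*The wording can be read sensibly.* Capture is the operative criterion, and the loss rule closes by referring to ascertaining outcomes. An analyst could treat the bracketed gloss as loose, and both faults would then disappear. But the gloss points to a defined rule that requires a visit and is not specific to any aim. A 36-week visit does ascertain the Aim 1 and 2 outcomes. The choice of reading should not be left until the data are in.

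*Other contacts recover birth outcomes.* Postpartum visits, calls, chart review and infant contacts will shrink the lesser fault, although Section XIV.b makes infant follow-up optional. They do not cure the main fault, because the rule does not count an outcome known only by phone or from the chart.

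*The adverse-outcome composite may not be primary.* Section III.a lists adverse birth outcomes as primary for Aim 3, while Appendix A puts the composite under secondary and names safety and mean birthweight as primary. This limits the weight of the point but leaves the mismatch in place.

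A reader might also infer that Section XIII promises too few births for Aim 3, since it says: "This will allow us to have 268 women with evaluable outcomes". The documents do not support that. The same sentence refers to the power calculation, which is Aim 1's, and the retention goal above 95% beside it makes no claim that birth outcomes are complete.

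**Conclusion.** The concern holds in a limited form. Read as written, one loss rule serves all aims, and through the per-protocol definition it excludes recorded early endings that are adverse by definition. It also lets a visit before birth count as capture. The affected items are ascertainment status, any per-protocol Aim 3 analysis and the reported loss figure.

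The number of women is probably small. The figure of 1 to 12 for the main fault rests on assumed ranges, not on trial data.

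Three stronger readings go beyond the documents:
- That birth outcomes are misclassified. No outcome value is altered; only whether a woman counts as ascertained.
- That the treatment comparison is biased by some stated amount. Nothing gives missingness or early endings by arm, and if they are similar in both arms the expected bias is small.
- That unknown 7-day vital status belongs to this point. Section VII.e says staff "plan to call after 7 days to ask about neonatal mortality", so that status can be missing even after a facility birth. How to score it is a separate missing detail, not a consequence of the loss rule.

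The change is worth making because it is cheap and removes a selection that depends on the result. It does not call the primary analysis into question.

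**What to change.** Define loss separately by aim in Section XII:

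- **Aims 1 and 2:** lost if there is no qualifying sample from the term, delivery or postpartum visit.
- **Aim 3:** lost if the pregnancy outcome is unknown from every source: chart, sick visit, delivery or postpartum visit, phone call and infant contacts. A term visit alone is not capture.

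In the per-protocol definition, replace the bracketed equation with loss by *outcome known for that aim*, whether good or bad, and keep the follow-up visit and adherence criteria as they are. Report the number of unknown outcomes by arm for each aim, in place of a single loss figure.

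The cost is wording only. Form 9 is already scheduled at the sick, term, delivery and postpartum visits and at the call, and infant contacts have their own form. The downside is that some outcomes, such as a gestation or birthweight given by phone, will rest on the mother's report. They should be flagged so that results can be shown with and without them.

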#### b) Secondary Outcomes

**Aim 1** a) Episodes of symptomatic malaria during study period; b) geometric mean parasite density at delivery; c) Proportion with placental malaria (impression smear, available on a subset); d) Proportion with anemia at delivery (hgb <11 g/dL); e) Proportion with adverse birth outcomes, including preterm delivery (<37 wks), stillbirth, low birth weight (<2500g) or early neonatal death (<7 days); f) Proportion of infants with poor growth at 6 and 12 months of age.

**Aim 2** a) Proportion with anogenital GBS colonization after 35 weeks GA or at delivery; and b) Maternal puerperal and/or neonatal infections prior to hospital discharge c) Proportion with infection with Mycoplasma genitalium (M gen), Trichomonas vaginalis (T vag), and bacterial vaginosis (BV).

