### a) Enrollment Visit

Following the provision of informed consent, study subjects will be randomized to one of two arms. A baseline survey will be administered by study nurses, vital signs will be collected and a brief exam will be performed. The medical chart will be reviewed for additional information. A 30 day supply of medications will be provided by study nurse. Contact information will be collected for the woman and a back-up person (with permission) and women will be given an appointment to return in 30 days. Bed nets, condoms and safe sex counseling will be provided. Partner HIV testing will be recommended, discussed with all women and facilitated, as necessary. Questions will be asked by study staff and entered into a RedCAP database. All forms will be labeled with the unique study ID, visit number and date.

Testing: CBC, thick smear and DBS. RPR confirmatory testing for those with + ANC syphilis screen. Vaginal swab for GC/CT and store. pH. Slides and store.

Treatment: For malaria peripheral parasitemia:

1st trimester – Quinine.

National Guidelines: Three doses of Parenteral Quinine base at 8.3mg/kg x 3 every 8 hours for 24 hours. Each infusion should run for 4 hours. This is relayed by Oral Quinine (tablets) for 3 days if patient can tolerate) and a maximum dose of 1.5 per day of Quinine base. The treatment is for 7 days. If the woman develops contractions on quinine, administer tocolytics.

2nd or 3rd trimester - Artesunate.

Per National Guidelines: Injectable Artesunate IV or IM: 2.4mg/kg at 0, 12, and 24 hours. This is continuous once every 24 hours until the patient can take the oral with ease. This is relayed with Artemether -Lumefantrine for 3 days if she can swallow.

1st dose of study medications will be given under directly observed therapy (DOT).

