### b) Scheduled Follow Up Visit

Subjects will have vitals and brief exam. If they are noted to be febrile (axillary T>37.5), RDT will be collected. Survey about medication adherence for ART, TMPS, AZ/placebo, pill count, tolerance of prophylaxis and ART, interim treatment, ITN usage. Transportation costs, 30 day medication supply and follow up appointment will be

provided. Contact information will be verified. Questions will be asked by study staff and entered into a RedCAP database.

Testing: DBS for all. RDT if febrile.

Treatment (dosing in section a)):

Malaria with positive RDT: Quinine during the 1st trimester, Artesunate IV during 2nd or 3rd trimester. STI rx from enrollment visit if needed. Syndromic management of STI per routine. DOT ppx meds. Condoms and safe sex counseling will be provided.

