**c) Unscheduled Sick Call Visit**

Per routine 24/7 in maternity unit. Vitals and brief exam. Management will be per routine with RDT for fever. Transportation costs will be covered.

If scheduled appointment had been missed – if possible, administer survey about medication adherence and tolerance and outside medications. Provide medications for 30 days. Questions will be asked by study staff and entered into a RedCAP database.

Testing: RDT for fever per routine, DBS for malaria testing (PCR)

Treatment (dosing in section a)):

Malaria with positive RDT: Quinine during the 1st trimester, Artesunate IV during 2nd or 3rd trimester. STI syndromic management. Other antibiotics per routine if recommended by provider and this will be captured as an outcome. DOT of prophylaxis medications if provided.

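### The imbalance-triggered parasitemia model is labelled as baseline factors but lists malaria treatment received and number of study visits, which arise partly or almost wholly after randomization

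*Combined protocol and SAP*

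**What the plan says.** Section XII (Statistical Analysis) makes the intention-to-treat comparison of parasitemia the primary analysis, with chi-square or Fisher tests for categorical outcomes. It then adds a multivariable regression to "evaluate baseline factors associated with parasitemia if there is imbalance between the arms despite randomization". The potential covariates include age, parity and other socio-demographic items, CD4 count, ART adherence and bed net usage, and the list ends with "malaria treatment received and number of study visits". No time point is given for any covariate, and the text does not say whether study arm is a term in the model.

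The timing comes from other sections:

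- **Randomization.** Section VII.a places it at the enrollment visit: after consent, "study subjects will be randomized to one of two arms".
- **Malaria at entry.** Women with active malaria may enroll (Section V.b), and parasitemia found at enrollment is treated (Section VII.a).
- **Malaria treatment later.** Scheduled follow-up and sick-call visits carry the same rule: "Malaria with positive RDT: Quinine during the 1st trimester, Artesunate IV during 2nd or 3rd trimester" (Section VII.c). The late-pregnancy visit has "Malaria with positive RDT: Artesunate IV (dosing above" (Section VII.d), and Section VII.e provides for treatment at delivery. The follow-up survey records "tolerance of prophylaxis and ART, interim treatment, ITN usage" (Section VII.b).
- **Visits.** The Section VII schedule has one enrollment visit, then 1-6 follow-up visits, 1-9 sick visits, a term visit and a delivery visit.
- **Outcomes.** "Episodes of symptomatic malaria during study period" is an Aim 1 secondary outcome (Section III.b).

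**The concern.** Randomization can leave a chance imbalance only in things fixed before it. A difference between arms in on-study malaria treatment, or in sick visits, may be an effect of azithromycin, which the trial expects to prevent malaria. As written, such a difference could trigger the model and then be adjusted away as if it were chance.

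Two mechanisms are at work. First, if treatment affects later parasitemia, adjusting for it moves the estimate from the total effect of assignment toward a direct effect. Second, exposure and susceptibility to malaria drive both on-study treatment and parasitemia at delivery. Conditioning on treatment then makes the arms differ in susceptibility within each treatment stratum, even if treatment has no effect on later parasitemia.

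There is also overlap with the outcome. A woman who is RDT- or smear-positive at 35-42 weeks or delivery is treated because of a result at the outcome visit. This does not apply to women positive only by PCR, which is run later from stored blood spots (Section X).

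The adjusted result would be read as support for the primary one. It could differ from the valid unadjusted result for reasons unrelated to chance imbalance.

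**Working it through.** **1. The plan's own figure.** The plan gives none for this model. Its design figure is 134 evaluable per arm for 30% vs 15%, 80% power, two-sided 0.05 (Section XI). With mean proportion 0.225:

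- n = [1.96 x sqrt(2 x 0.225 x 0.775) + 0.8416 x sqrt(0.30 x 0.70 + 0.15 x 0.85)]^2 / 0.15^2 = (1.1575 + 0.4889)^2 / 0.0225 = 120.5, so 121.
- With continuity correction: (120.5 / 4) x [1 + sqrt(1 + 4 / (120.5 x 0.15))]^2 = 133.5, so 134.

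The figure reproduces. It belongs to the unadjusted test and does not depend on this model.

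**2. Timing of the two covariates.**

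| Covariate | Part fixed at entry | Part arising after randomization |
|---|---|---|
| Malaria treatment | Treatment of infection found at enrollment | Treatment at follow-up, sick-call, 35-42-week and delivery visits |
| Number of visits | The enrollment visit, the same for every woman | All variation; scheduled visits follow largely from gestational age at entry, sick visits from illness |

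**3. Size of the effect of adjusting for treatment.** From the documents: parasitemia 30% vs 15%, a true difference of -15.0 points. Assumed: the treatment rates (azithromycin arm treated half as often), a normal susceptibility U with SD 1, 1.5 or 2, and an effect g of earlier treatment on later parasitemia.

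- Treatment M: logit P(M) = a_arm + U
- Parasitemia Y: logit P(Y) = b_arm + U + g x M
- a_arm and b_arm are solved in each arm, by 121-point Gauss-Hermite integration, to give the treatment rate and 30% or 15% parasitemia
- Adjusted analysis: logistic Y ~ arm + M, standardized over the pooled distribution of M

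One cell in full (30%/15% treated, g = 0, SD 2). Parasitemia in controls is 18.74% if untreated and 56.26% if treated; in the azithromycin arm it is 10.17% and 42.37%. These return the planned totals: 0.70 x 18.74 + 0.30 x 56.26 = 30.0 and 0.85 x 10.17 + 0.15 x 42.37 = 15.0. Within strata the differences are -8.57 and -13.89 points. Pooled, 77.5% are untreated and 22.5% treated, so the adjusted difference is 0.775 x (-8.57) + 0.225 x (-13.89) = -9.8, against a true -15.0.

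Adjusted difference in points, for SD 1 / 1.5 / 2:

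| Treated, control/AZ | g = 0 | g = -1 | g = -2 |
|---|---|---|---|
| 30% / 15% | -13.0 / -11.3 / -9.8 | -15.3 / -13.7 / -12.0 | -17.2 / -15.7 / -14.1 |
| 20% / 10% | -13.6 / -12.4 / -11.2 | -15.2 / -14.0 / -12.8 | -16.4 / -15.4 / -14.3 |
| 10% / 5% | -14.2 / -13.5 / -12.9 | -15.1 / -14.4 / -13.7 | -15.6 / -15.1 / -14.5 |
| 5% / 2.5% | -14.6 / -14.2 / -13.9 | -15.0 / -14.7 / -14.3 | -15.3 / -15.0 / -14.7 |
| 2% / 1% | -14.8 / -14.7 / -14.5 | -15.0 / -14.8 / -14.7 | -15.1 / -15.0 / -14.8 |

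At g = 0 there is no shift toward a direct effect, and every cell moves toward the null. At g = -1 and -2 part of the movement is that shift. With equal treatment rates in the arms (30%, 10% or 5% in both) the difference stays -15.0, yet the odds ratio can go from 0.41 to 0.36 through non-collapsibility. Odds-ratio shifts on this grid are therefore not read as bias.

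**4. No drug effect.** With 20% parasitemia in both arms and g = 0, adjusting creates a false difference against azithromycin of 2.0 to 5.1 points at 30%/15% treated and 0.4 to 1.1 points at 5%/2.5%.

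**5. Visit count.** Simulation of 400,000 women: entry uniform over 8-28 weeks; scheduled visits every 4 weeks to week 35; Poisson sick visits with log-rate slope 0.5 on U, capped at 9. The shift toward the null for SD 1 / 1.5 / 2 is 1.0 / 2.0 / 2.7 points at a mean of 1.0 vs 0.5 sick visits per woman, 0.1 / 0.2 / 0.4 at 0.3 vs 0.15, and below 0.1 at equal rates.

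**The case against.** **Arm is not named.** Read literally, the sentence describes a risk-factor model. Without arm in it, none of the figures above applies. This stands as a limit. However, a trigger based on imbalance between arms has little purpose unless the arms are then compared, and the label and the list conflict on either reading.

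**The model is conditional and supportive.** It runs only on imbalance, the covariates are potential ones, and no primary conclusion depends on it. This is correct and limits the severity.

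**The size is assumed and may be small.** The documents give no on-study treatment rate. RDT at scheduled follow-up is limited ("Testing: DBS for all. RDT if febrile"), and every woman receives daily TMPS and a bed net. With 10% or fewer controls treated, the largest shift is 15.0 - 12.9 = 2.1 points. The standard error of the difference at 134 per arm is sqrt[(0.30 x 0.70 + 0.15 x 0.85) / 134] = 5.0 points, so the shift is under half a standard error. Weaker shared causes shrink it further: at SD 0.5 and g = 0 the adjusted differences are -14.4, -14.8 and -14.9 at 30%, 10% and 5% of controls treated. This too stands, except that weaker shared causes do not remove the movement when treatment clears infection: the same formulas at SD 0.5, g = -2 and 30%/15% treated give -18.1.

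**Visit count is the weaker half.** Section XII does not define study visits. If sick visits are excluded, the count follows largely from gestational age at entry. A separate simulation, with one extra visit per treated episode, moved the odds ratio by 0.01 or less. It remains true that visit count cannot be a baseline value.

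**The word baseline may already govern the list.** That is a fair reading for CD4 count, ART adherence and bed net usage. It cannot rescue visit count, and nothing limits malaria treatment to enrollment.

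**Conclusion.** The point holds and should be fixed. The model's label and covariate list contradict each other: one listed variable is partly post-randomization and the other almost wholly so, and azithromycin can affect both. In an adjusted arm comparison this can bias the estimate in either direction.

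For treatment, the illustrated range runs from -9.8 to -17.2 points around a true -15.0 at 30%/15% treated, and narrows to -14.5 to -15.1 at 2%/1%. Visit count shifts the estimate by 0.1 to 2.7 points under the unequal sick-visit rates tried. These sizes rest on assumed treatment and visit rates, on the assumed strength of shared causes (SD 1 to 2), and on arm being a model term. The contradiction in the text rests on none of them. The primary intention-to-treat test, its power and the sample size are unaffected.

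**What to change.** In Section XII (Statistical Analysis):

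- Delete on-study malaria treatment and number of study visits from the covariate list.
- State whether arm is a term in the model.
- Restrict the adjusted model to values recorded at or before enrollment, and say so for CD4 count (chart value where available), ART adherence and bed net usage.
- Use enrollment parasitemia, from the thick smear and blood spot already collected at that visit, to represent malaria at entry.
- Optionally add site, the stratification factor (Section V.d). If visit count was meant to stand for duration of prophylaxis, gestational age at entry is the baseline variable that does so.
- Report on-study malaria treatment and visit counts by arm descriptively.

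The cost is the wording of two sentences. No visit, test or sample size changes. The one drawback is that baseline CD4 depends on what the chart holds, because the schedule table, as it could be read, marks study CD4 only at the term visit.
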